## 7 SELECTION OF PATIENTS

### 7.1 INCLUSION CRITERIA

- I 01. Adults and adolescent patients with a physician diagnosis of asthma for  $\geq 12$  months, based on the Global Initiative for Asthma (GINA) 2014 Guidelines and the following criteria:
- A) Existing treatment with medium to high dose ICS ( $\geq 250$  mcg of fluticasone propionate twice daily or equipotent ICS daily dosage to a maximum of 2000 mcg/day of fluticasone propionate or equivalent) in combination with a second controller (eg, LABA, LTRA) for at least 3 months with a stable dose  $\geq 1$  month prior to Visit 1.
    - Note for Japan: for subjects aged 18 years and older, ICS must be on  $\geq 200$  mcg of fluticasone propionate twice daily or equivalent; for subjects aged 12 to 17 years, ICS must be  $\geq 100$  mcg of fluticasone propionate twice daily or equivalent.
    - Patients requiring a third controller for their asthma will be considered eligible for this study, and it should also be used for at least 3 months with a stable dose  $\geq 1$  month prior to Visit 1.
  - B) Pre-bronchodilator forced expiratory volume ( $FEV_1$ )  $\leq 80\%$  of predicted normal for adults and  $\leq 90\%$  of predicted normal for adolescents at Visits 1 and 2, prior to randomization.
  - C) Asthma Control Questionnaire 5-question version (ACQ-5) score  $\geq 1.5$  at Visits 1 and 2, prior to randomization.
  - D) Reversibility of at least 12% and 200 mL in  $FEV_1$  after the administration of 200 to 400 mcg albuterol/salbutamol or levalbuterol/levosalbutamol (2 to 4 inhalations of albuterol/salbutamol or levalbuterol/levosalbutamol, or of a nebulized solution of albuterol/salbutamol or levalbuterol/levosalbutamol, if considered as a standard office practice) before randomization.
  - E) Must have experienced, within 1 year prior to Visit 1, any of the following events:
    - Treatment with a systemic steroid (oral or parenteral) for worsening asthma at least once.
    - Hospitalization or emergency medical care visit for worsening asthma.
- I 02. Signed written informed consent.

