1.3 DETERMINATION OF SAMPLE SIZE

The sample size was calculated on a comparison between dupilumab 300 mg q2w versus placebo with regard to the 2 primary endpoints: annualized rate of severe asthma exacerbations during the 52-week treatment period, and absolute change from baseline in FEV1(L) at Week 12. Assuming the number of severe asthma exacerbations follows a negative binomial distribution with a dispersion parameter of 2, a placebo annualized rate of exacerbations being 0.6, a randomization ratio of 2:2:1:1, with 1638 randomized patients (546 for each dupilumab dose and 273 for each matching placebo group), the study will have 99% power to detect a 55% relative risk reduction (ie, annualized rate of 0.27 for the dupilumab group) in the annualized rate of severe asthma exacerbations at the 2-tailed significance level of $\alpha=0.05$. Assuming 42% patients with a baseline blood eosinophil count ≥ 0.3 Giga/L, approximately 690 patients (230 for dupilumab 300mg q2w and 115 for the matching placebo) will provide 91% power to detect a 55% relative risk reduction for this subgroup. Assuming a common standard deviation of 0.5 L, 1638 patients (546 for each dupilumab dose and 273 for each matching placebo group) will provide 98% power to detect a treatment difference of 0.15 L in the change of FEV1 from baseline at Week 12 for the overall population, and 690 patients (230 for dupilumab 300mg q2w and 115 for the matching placebo) will provide 88% power to detect a treatment difference of 0.18 L for patients with a baseline blood eosinophil count ≥ 0.3 Giga/L. The overall study recruitment will continue until at least 1638 patients in total and 690 patients with blood eosinophils ≥ 0.3 Giga/L are randomized. The recruitment for patients on treatment of medium dose of ICS will stop when approximately 819 patients in this category have been randomized into the study. In addition, approximately 84 adolescent patients will be randomized.

In addition to the originally planned sample size of 1638 patients, approximately 220 patients will be randomized in order to have additional patients treated with the drug product manufactured using the intended commercial process.

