Comorbidity history will be summarized separately. The following comorbid diseases will be summarized.

- Atopic dermatitis history (Yes, Ongoing condition)
- Allergic conjunctivitis history (Yes, Ongoing condition)
- Allergic rhinitis history (Yes, Ongoing condition)
- Allergic conjunctivitis and/or rhinitis history (Yes, Ongoing condition)
- Chronic rhinosinusitis history (Yes, Ongoing condition)
- Nasal polyposis history (Yes, Ongoing condition)
- Eosinophilic esophagitis history (Yes, Ongoing condition)
- Food allergy history (Yes, Ongoing condition)
- Hives history (Yes, Ongoing condition)

A patient is considered to have atopic medical condition if he/she has any of the following: atopic dermatitis, allergic conjunctivitis or rhinitis, eosinophilic esophagitis, food allergy, hives; or has baseline total IgE ≥ 100 IU/mL and at least one aeroantigen specific IgE is positive (≥ 0.35 IU/mL) at baseline.

Disease characteristics at baseline

The following baseline disease characteristics will be summarized by treatment group separately:

- ICS dose level (medium, high as defined in [Appendix C](#))
 - Age of asthma onset
 - Time since first diagnosis of asthma (years)
 - Smoking history (Never, Former*), time since cessation of smoking (months) and smoking quantity in pack-years for former smokers
- * Current smokers are excluded from this study.*
- Time since last severe asthma exacerbation (months)
 - Number of severe asthma exacerbation experienced within 1 year before Visit 1 (quantitative variable and qualitative variable: 0, 1, 2, 3, ≥ 4)
 - Eosinophil stratum at randomization (< 0.3 , ≥ 0.3 Giga/L)

- Baseline spirometry data including pre-bronchodilator FEV1 (L), percent predicted FEV1, post-bronchodilator FEV1 (L) and FEV1 reversibility (%).
- AM and PM PEF (L/min)
- AM and PM symptom scores
- Number of nocturnal awakenings/night
- ACQ-5 score
- ACQ-7 score
- AQLQ global score
- Number of inhalations of salbutamol/albuterol and levosalbutamol/levabuterol per day
- Hypersensitivity to aspirin/NSAID (Yes, Ongoing condition)

Severe asthma exacerbation prior to the study is defined as any treatment with 1 systemic (oral or parenteral) steroid bursts or more for worsening asthma or hospitalization or an emergency/urgent medical care visit for worsening asthma. Any technical details related to computation, dates, and imputations for missing dates are described in [Section 2.5](#).

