The primary analysis of change from baseline in pre-BD FEV₁ at Week 12 is to assess the efficacy of dupilumab in a real-world setting. The absolute change from baseline in FEV₁ at Week 12 will be analyzed using a mixed-effect model with repeated measures (MMRM) approach. The model will include change from baseline in pre-BD FEV₁ values up to Week 12 as response variables, and treatment, age, sex, baseline height, region (pooled country), baseline eosinophil strata, baseline ICS dose level, visit, treatment by-visit interaction, baseline pre-BD FEV₁ value and baseline-by-visit interaction as covariates. Treatment groups, sex, region, baseline eosinophil strata, baseline ICS dose level, and visit will be treated as categorical variables. Age and height will be treated as continuous variable. For patients who discontinue the treatment before Week 12, they will be asked and encouraged to return to the clinic for all remaining study visit and the additional off study-treatment pre-BD FEV₁ values measured up to Week 12 will be included in the primary analysis. For patients who withdraw from the study before Week 12, pre-BD FEV₁ values will be missing after study discontinuation. No imputation will be performed for missing values in the primary analysis. This estimand compares the change from baseline in pre-BD FEV₁ for the patients randomized to the dupilumab and placebo arms, regardless of what treatment patients actually received. It assesses the benefits of the treatment policy or strategy relative to placebo (7).

An unstructured correlation matrix will be used to model the within-patient errors. Parameters will be estimated using restricted maximum likelihood method with the Newton-Raphson algorithm. Statistical inferences on treatment comparisons for the change from baseline in pre-BD FEV₁ at Week 12 will be derived from the mixed-effect model. Difference in LS mean change from baseline, the corresponding 95% CI and the p-value with Kenward-Roger adjustment will be provided for comparison for each dupilumab group against its matching placebo. In addition, descriptive statistics including number of patients, mean, standard error and LS mean of change from baseline will be provided.

A sample SAS code can be found below:

```
proc mixed data=adsd.adre method=reml;
  where paramcd='FEV1' and avisitn ge 3 and avisitn le 8 and ittfl='Y';
  class subjid sex eosblgpn ics trt01pn avisitn cntygrln;
  model chg = trt01pn sex age height ics eosblgpn cntygrln avisitn

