2.4.4.3 Multiplicity issues

To strongly control the type-I error rate for the primary family (two primary endpoints and two doses), a hierarchical testing procedure will be applied at a 2-sided 5% significant level, ie, each hypothesis will be formally tested only if the preceding one is significant at the 5% level. The hierarchy of the tests will be: 1) annualized severe exacerbation rate for 300 mg q2w versus placebo, 2) absolute change from baseline in FEV1 at Week 12 for 300 mg q2w versus placebo, 3) annualized severe exacerbation rate for 200 mg q2w versus placebo, 4) absolute change from baseline in FEV1 at Week 12 for 200 mg q2w versus placebo.

If both doses are significant for both primary endpoints, a selective set of secondary endpoints will be tested following a hierarchical testing procedure at a 2-sided 5% significant level. The complete list of the endpoints with their testing order is specified in [Table 6](#).

Table 6 – Hierarchical testing order

Endpoints		Dupilumab	
		200 mg q2w	300 mg q2w
Primary endpoints	Annualized rate of severe exacerbation events during the 52-week treatment period - ITT population	3	1
	Change from baseline in pre-bronchodilator FEV ₁ at Week 12 - ITT population	4	2
Secondary endpoints	Percent change from baseline in pre-bronchodilator FEV ₁ at Week 12 - ITT population	11	5
	Annualized rate of severe exacerbation events during the 52-week treatment period - ITT population with baseline eosinophil ≥ 0.15 Giga/L	12	6
	Change from baseline in pre-bronchodilator FEV ₁ at Week 12 - ITT population with baseline eosinophil ≥ 0.15 Giga/L	13	7
	Annualized rate of severe exacerbation events during the 52-week treatment period - ITT population with baseline eosinophil ≥ 0.3 Giga/L	14	8
	Change from baseline in pre-bronchodilator FEV ₁ at Week 12 - ITT population with baseline eosinophil ≥ 0.3 Giga/L	15	9
	Annualized rate of severe exacerbation events during the 52-week treatment period - ITT population with baseline eosinophil < 0.3 Giga/L	16	10
	Annualized rate of severe exacerbation events during the 52-week treatment period - ITT population with high dose ICS at baseline	22	17
	Change from baseline in pre-bronchodilator FEV ₁ at Week 12 - ITT population with high dose ICS/LABA at baseline	23	18
	Change from baseline in AQLQ global score at Week 24 - ITT population	24	19
	Change from baseline in AQLQ global score at Week 24 - ITT population with baseline eosinophil ≥ 0.3 Giga/L	25	20

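### The primary Week 12 FEV1 model does not adjust for baseline post-bronchodilator FEV1, so the treatment difference may be estimated less precisely than the collected data allow

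*SAP*

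**What the plan says.** SAP 2.4.4.1.2 gives the covariates as "treatment, age, sex, baseline height, region (pooled country), baseline eosinophil strata, baseline ICS dose level, visit, treatment by-visit interaction", followed by baseline pre-bronchodilator FEV1 and baseline-by-visit. The sample SAS code in that section has the same terms, and Protocol 11.4.2.1 lists the same set. Neither post-bronchodilator FEV1 nor reversibility appears.

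The measurement exists before randomization:

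- Protocol 7.1 makes bronchodilator response an entry condition: "Reversibility of at least 12% and 200 mL in" FEV1.
- The flow chart (Protocol 1.2) and Protocol 10.1.2 schedule a post-bronchodilator FEV1 at Visit 2.
- SAP 2.1.1 lists it among the baseline characteristics: "Baseline spirometry data including pre-bronchodilator FEV1 (L), percent predicted FEV1, post-bronchodilator FEV1 (L) and FEV1 reversibility".
- SAP Table 9 gives post-bronchodilator spirometry a Visit 2 window that takes any value up to randomization and before the first dose.
- SAP 2.4.4.2.1 already uses baseline post-bronchodilator FEV1 as a covariate in the model for post-bronchodilator FEV1 slope.

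On power, SAP 1.3 splits the planned 1638 as "546 for each dupilumab dose and 273 for each matching placebo group". For the overall population, it says that this sample "will provide 98% power to detect a treatment difference of 0.15 L". For patients with eosinophils of at least 0.3 Giga/L, it says that the planned 690 "will provide 88% power to detect a treatment difference of 0.18 L". Both rest on the same premise: "Assuming a common standard deviation of 0.5 L".

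**The concern.** Patients enter with a low pre-bronchodilator FEV1 at Visits 1 and 2, and the baseline is the last single value before dosing. Some of those values will be temporarily low for that patient. Age, sex and height describe the lung function expected in a population; a post-bronchodilator value in litres says something about what the individual can reach. If it predicts Week 12 change beyond the terms already in the model, leaving it out gives a wider confidence interval than necessary.

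The stake lies less in the overall primary test than in the fixed testing sequence of SAP 2.4.4.3. FEV1 in the high-eosinophil group is step 9 (300 mg) and step 15 (200 mg) of 30. Its 88% is the lowest power that the SAP states for any comparison. A miss at step 9 ends formal testing of the 21 hypotheses after it.

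**Working it through.** **Inputs from the documents.** SD 0.5 L; difference 0.15 L with 546 v 273 (overall) and 0.18 L with 230 v 115 (eosinophils of at least 0.3 Giga/L), all from SAP 1.3. Each dose is compared with its own matching placebo (SAP 2.4.4.1.2). For alpha, "a hierarchical testing procedure will be applied at a 2-sided 5% significant level" (SAP 2.4.4.3), so there is no split.

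**Reproducing the stated power.** Power = Φ(d/SE − 1.96), with SE = 0.5 × √(1/n₁ + 1/n₀).

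- Overall: SE = 0.5 × √(1/546 + 1/273) = 0.0371 L; 0.15/0.0371 = 4.05; power 98.16% (stated 98%).
- High eosinophils: SE = 0.5 × √(1/230 + 1/115) = 0.0571 L; 0.18/0.0571 = 3.15; power 88.34% (stated 88%).

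A noncentral t calculation gives 98.14% and 88.17%. Both stated figures reproduce.

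**Effect of the extra covariate.** Let r be the partial correlation of baseline post-bronchodilator FEV1 with Week 12 change, given the covariates already in the model. The residual SD becomes 0.5 × √(1 − r²), and the equivalent gain in patients is 1/(1 − r²) − 1. The documents do not give r, so the range is assumed.

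| Assumed r | SE reduction | Equivalent extra patients | Overall 95% CI half-width (L) | Power, overall | Power, high eosinophils |
|---|---|---|---|---|---|
| 0 | 0% | 0% | 0.0726 | 98.16% | 88.34% |
| 0.1 | 0.5% | 1.0% | 0.0723 | 98.25% | 88.65% |
| 0.2 | 2.0% | 4.2% | 0.0712 | 98.50% | 89.57% |
| 0.3 | 4.6% | 9.9% | 0.0693 | 98.88% | 91.06% |
| 0.4 | 8.3% | 19.0% | 0.0666 | 99.30% | 93.05% |

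**Cost if r is zero.** One extra slope at Week 12 inflates the SE by a factor of about √(1 + 1/816) = 1.0006 with 819 patients in the comparison. Break-even is r = √(1/817), about 0.035.

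**The two high-eosinophil FEV1 steps together.** Suppose the 0.18 L effect and 230 v 115 also hold for 200 mg, and treat the two comparisons as independent because each dose has its own placebo. The chance that both succeed is then 0.8834² = 78% at r = 0, 0.8957² = 80% at 0.2, 0.9106² = 83% at 0.3 and 0.9305² = 87% at 0.4.

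**Form of the term.** The full reduction of 1 − r² at Week 12 follows from a main effect alone only if the covariate acts equally at every visit. The plan gives its own baseline value an interaction with visit; the same treatment is needed here. With six post-baseline visits in the model (Weeks 2, 4, 6, 8, 10 and 12), that makes six parameters: one main effect and five interaction terms.

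**The case against.** The strongest case against is that this is a preference, not a defect. The protocol and SAP agree on the covariates, which cover the stratification factors (with country pooled into region) and the baseline of the outcome with its visit interaction. Those terms already absorb much of the upward drift of patients who start low. Nothing in the documents shows that post-bronchodilator FEV1 adds to them. The entry criteria also narrow what it could add: every eligible patient must show at least 12% and 200 mL of reversibility, and COPD and other lung disease that may impair lung function are excluded. The test itself varies (two to four puffs or a nebulizer, with up to three screening assessments). Other baseline values, such as ACQ-5 or FeNO, could be proposed on similar grounds.

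Most of this stands as a limit on the likely gain and is the reason for including r = 0 in the range. It does not remove the point. The 12% and 200 mL threshold applies to the qualifying test; a patient who qualified earlier has a separate Visit 2 value that need not meet it. The proposed covariate is in litres, so it does not share the pre-bronchodilator denominator that percent reversibility has. Unlike the other candidates, it is a spirometry measure that the SAP already derives and enters in another model. That use shows only that the variable is available: in the slope model it is the baseline of the outcome itself, so it is no evidence that it predicts pre-bronchodilator change.

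A reader might infer that a loss of precision is established. The documents do not support that, because they give no value for r.

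**Conclusion.** This is an optional efficiency improvement. The primary FEV1 model omits a pre-randomization spirometry value that the trial collects in any case, and the Week 12 difference may therefore be less precise than it could be. Over the assumed range of r from 0 to 0.4, the gain is 0 to 4.7 percentage points of power in the high-eosinophil comparison (88.34% to 93.05%) and 0 to 1.1 points overall (98.16% to 99.30%).

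The figures rest on the plan's own simplification of a two-group comparison at Week 12 without dropout, on the planned 1638 patients without the approximately 220 added later, and on 0.5 L being the residual SD under the present model. The SAP does not say whether 0.5 L is before or after adjustment.

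Two stronger readings should be resisted. The omission does not bias the treatment difference or inflate type I error, since the comparison is randomized and the model linear. Nor is the primary FEV1 test underpowered: at the stated assumptions it has 98% whether or not the term is added.

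**What to change.** Before database lock and unblinding, add baseline post-bronchodilator FEV1 in litres, with its interaction with visit, to:

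- the primary pre-bronchodilator FEV1 MMRM and its subgroup versions;
- the percent-change MMRM for the key secondary endpoint;
- the matching multiple-imputation and ANCOVA sensitivity models, where the ANCOVA needs only the main effect.

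Take the value under the existing Table 9 rule (last value up to randomization), so that a screening reversibility test serves when the Visit 2 test is missing. State this in the SAP, because a few patients randomized in error could lack a qualifying test. Keep the present model as a sensitivity analysis and record the change in SAP 1.6.

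The cost is a short SAP edit, a few extra parameters, and an older baseline value for patients without a Visit 2 test. No new data are needed.

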trt01p*avisitn base base*avisitn/ddfm=kr residual;
  repeated avisitn/type=un subject=subjid;
  lsmeans trt01pn*avisitn /pdiff cl ;
  estimate '300 mg q2w vs Placebo 2ml q2w at Week 12 Visit 8'
trt01pn 0 -1 0 1 trt01pn*avisitn 0 0 0 0
0 0 0 -1
0 0 0 0
0 0 0 1/ cl;
run;
```

If MMRM model fails to achieve convergence due to complexity of model specification, we may add some procedures to handle this issue including: 1) using maximum likelihood estimation instead of restricted maximum likelihood method; 2) covariance structure selection to reduce the number of unknown parameters to be estimated, the path is UN→TOEPH→TOEP→AR(1)→CS. The adjustment will be added to the footnote of the corresponding outputs.

Estimand of clinical efficacy of dupilumab versus placebo

To assess the treatment effect when the patients adhere to the study treatment as directed, on-treatment pre-BD FEV1 measurements will be analyzed using the similar MMRM model as for the primary analyses, including same set of covariates and estimation algorithm. The model will include on-treatment change from baseline in pre-BD FEV1 values up to Visit 8 (Week 12) as response variables. A pre-BD FEV1 value is considered as on-treatment if it's measured before or on the last dose date + 14 days.

Sensitivity analyses with different censoring methods for pre-BD FEV1 potentially confounded by systemic corticosteroid use

In addition, two sets of sensitivity analyses with different methods of handling pre-BD FEV1 measurements confounded by the systemic corticosteroid use will be performed:

- Censoring method 1: pre-BD FEV1 measurements collected from systemic corticosteroid start date to systemic corticosteroid end date + 14 days will be excluded in order to reduce the confounding effect of systemic corticosteroids
- Censoring method 2: All pre-BD FEV1 measurements collected on and after first day of systemic corticosteroid use will be excluded.

The above two censoring methods will be applied to both primary analyses and on-treatment analysis. On-treatment analysis with data censoring method 1 will be used to provide treatment effect size estimates without confounding effect of systemic corticosteroid use.

Handling of missing data

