2.4.4.2 Analyses of secondary efficacy endpoints

2.4.4.2.1 Absolute/percent change from baseline for continuous endpoints

The key secondary endpoint, percent change from baseline in pre-bronchodilator FEV1 at Week 12, will be analyzed in the same way as for change from baseline in FEV1 at Week 12, with the only difference that percent changes, instead of absolute changes, from baseline in FEV1 up to Week 12 will be included as the response variables. MMRM model including measurements up to Week 52 will also be used to derive LS mean change at all time-points. Differences in LS means, the corresponding 95% CI and the p-value will be provided for comparisons of each dupilumab dose against its matching placebo along with descriptive statistics.

Change from baseline in ACQ-5 and AQLQ at Week 24 will be analyzed using MMRM including change from baseline up to Week 24 as response variables, regardless if the patient is on treatment or not when the endpoint is measured. The model will include treatment, age, region (pooled country), baseline eosinophil strata, baseline ICS dose level, visit, treatment by-visit interaction, baseline endpoint value, and baseline-by-visit interaction as covariates. MMRM model including measurements up to Week 52 will also be used to derive LS mean change at all time-points. Differences in LS means, the corresponding 95% CI and the p-value will be provided for comparisons of each dupilumab dose against its matching placebo along with descriptive statistics.

Change from baseline in other continuous endpoint at all time-points will be analyzed using MMRM model including measurements up to Week 52. The model will include change from baseline in the endpoint values from Week 2 to Week 52 as response variables, regardless if the patient is on treatment or not when the endpoint is measured, and treatment, age, sex, baseline height, region (pooled country), baseline eosinophil strata, baseline ICS dose level, visit, treatment by-visit interaction, baseline endpoint value and baseline-by-visit interaction as covariates. Sex and baseline height will be included as covariates only in the models for spirometry parameters. Differences in LS means, the corresponding 95% CI and the p-value will be provided for comparisons of each dupilumab dose against its matching placebo along with descriptive statistics.

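### The MMRM non-convergence path ends in common-variance structures with no empirical variance named; if it is used that far and the SD rises over visits, the last-visit test exceeds 5%

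*SAP*

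**What the plan says.** The primary FEV1 model (SAP 2.4.4.1.2) is an MMRM on Visits 3 to 8 (Weeks 2, 4, 6, 8, 10 and 12) with an unstructured covariance, REML and Kenward-Roger inference. The sample code requests no empirical variance.

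If the model fails to converge, the section permits two measures, in permissive wording:

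- "using maximum likelihood estimation instead of restricted maximum likelihood method";
- "covariance structure selection to reduce the number of unknown parameters to be estimated", along the path UN, TOEPH, TOEP, AR(1), CS.

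Any such change is to be footnoted in the output. The section does not say whether ML is tried before a simpler structure or together with one, whether Kenward-Roger is kept under ML, or which variance estimator goes with the simpler structures.

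Other models follow the same approach. Protocol 11.4.2.1.3 analyses other continuous endpoints in the same way as FEV1. SAP 2.4.4.2.1 fits ACQ-5 up to Week 24, and Table 6 ranks that test 21 (300 mg) and 26 (200 mg). For the percent-change, ACQ-5 and AQLQ endpoints, SAP 2.4.4.2.1 adds that an "MMRM model including measurements up to Week 52 will also be used to derive LS mean change at all time-points". SAP 2.4.4.1.2 also fits a separate MMRM within each subgroup. SAP Table 2 records that the fallback was added in version 2 and refers to MMRM models in the plural.

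For the ranked tests, "a hierarchical testing procedure will be applied at a 2-sided 5% significant level" (SAP 2.4.4.3).

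**The concern.** TOEP, AR(1) and CS estimate a single variance for all visits. If the spread of the change from baseline grows with time, that pooled variance lies below the variance at the last visit, and in the Week 12 FEV1 and Week 24 ACQ-5 models the last visit is the one tested. A model-based standard error is then too small, the confidence interval too narrow and the p-value too low. An empirical variance would correct the standard error, but the plan does not call for one. At stake is the 5% level of any ranked test reached by this route, and the width of the reported intervals in the subgroup and longer models.

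**Working it through.** **Inputs from the documents.** Two-sided 5% (SAP 2.4.4.3). From SAP 1.3: "Assuming a common standard deviation of 0.5 L" and "546 for each dupilumab dose and 273 for each matching placebo group". Six visits in the primary model (sample code, SAP 2.4.4.1.2).

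**Inputs assumed.** The documents give no SD by visit. I fix the Week 12 SD at the stated 0.50 L and vary the Week 2 SD from 0.55 to 0.35 L, linear across the six visits. The documents give no dropout rate before Week 12, so 0%, 5% and 10% are used.

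**Step 1: the plan's own power figures.** The SAP says its sample "will provide 98% power to detect a treatment difference of 0.15 L in the change of FEV1 from baseline at Week 12", and that 690 patients "will provide 88% power to detect a treatment difference of 0.18 L".

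- 546 vs 273: SE = 0.5 × √(1/546 + 1/273) = 0.0371 L; 0.15/0.0371 = 4.05; power = Φ(4.05 − 1.96) = 98.2%.
- 230 vs 115: SE = 0.5 × √(1/230 + 1/115) = 0.0571 L; 0.18/0.0571 = 3.15; power = Φ(3.15 − 1.96) = 88.3%.

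Both reproduce. The plan states no error rate for the fallback, so there is nothing further to match.

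**Step 2: level under a common variance.** With complete data, a CS fit estimates the variance as the mean of the visit variances. The ratio of the model-based to the true Week 12 SE is R = √(mean variance / Week 12 variance), and the actual level is 2 × (1 − Φ(1.96 × R)).

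Worked case, Week 2 SD 0.40 L. The SDs are 0.40, 0.42, 0.44, 0.46, 0.48 and 0.50. The variances sum to 1.222, with mean 0.2037, against 0.25 at Week 12. R = √(0.2037/0.25) = 0.903, so the SE is about 10% too small (0.0335 instead of 0.0371 L). Level = 2 × (1 − Φ(1.769)) = 7.7%.

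| Week 2 SD (L) | Mean variance | R | Level, CS, complete data | Range: TOEP, AR(1), CS; 0–10% dropout; three correlation patterns |
|---|---|---|---|---|
| 0.55 | 0.2759 | 1.051 | 3.9% | 3.8–4.3% |
| 0.50 | 0.2500 | 1.000 | 5.0% | 4.9–5.4% |
| 0.45 | 0.2259 | 0.951 | 6.2% | 6.1–6.7% |
| 0.40 | 0.2037 | 0.903 | 7.7% | 7.6–8.2% |
| 0.35 | 0.1833 | 0.856 | 9.3% | 9.2–10.0% |

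The last column uses the large-sample limit of the likelihood fit for each structure. TOEPH gives 5.0% in every case.

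**Step 3: simulation.** With 8000 trials per case at 546/273/546/273, complete data and a CS fit, the level is 5.4%, 6.1%, 8.1% and 9.5% for Week 2 SD 0.50, 0.45, 0.40 and 0.35 L. With sandwich standard errors on the same fits it is 5.0–5.6% (simulation error about 0.25 points).

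**Step 4: the ML step.** Using ML for REML adds about 0.1 point at N = 1638 and 0.2–0.3 points at N = 690.

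**Step 5: nine visits to Week 24 (ACQ-5).** Visits 3 to 11 give 9 × 10/2 = 45 unstructured parameters, against 6 × 7/2 = 21 for the primary model. Assume a 25% rise in SD from Week 2 to Week 24 (relative SD 0.80 to 1.00). If the rise is linear in weeks, the mean variance is 0.787, R = 0.887 and the level is 8.2%. If it is linear by visit, these are 0.814, 0.902 and 7.7%. With constant SD the level is 5%.

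**The case against.** The case against acting has several parts.

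- **TOEPH comes first.** It allows a variance for each visit and holds 5%. Inflation needs UN and TOEPH both to fail, and also a rising SD. For 21 parameters and at least 1638 patients, that is unlikely. This stands, and it sets the low priority.
- **The SD pattern is not in the documents.** This stands. A constant SD leaves the level at about 5%, and a falling SD makes the test slightly conservative.
- **A check exists.** The multiple-imputation sensitivity analyses for FEV1 (SAP 2.4.4.1.2) use an ANCOVA at Week 12 alone, so their residual variance is not pooled over visits. A result created by pooling should show up there. This stands for the primary FEV1 endpoint; the SAP specifies no such analysis for ACQ-5.
- **A sandwich variance is not a full repair.** It corrects the standard error, but not the point estimate when data are missing at random and the covariance is wrong. It also gives up Kenward-Roger, which matters in small subgroups. This stands, and it is why a heterogeneous structure is the better first choice.

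Some stronger readings are tempting but unsupported. A reader might infer that moving to ML is itself a threat to the level; Step 4 shows it is immaterial at these sizes, and the SAP attaches the aim of reducing parameters only to the covariance step. A reader might carry the concern to confirmatory claims at Week 52, where the model has 16 visits and 16 × 17/2 = 136 unstructured parameters; but Table 6 ranks no continuous endpoint at Week 52. A reader might also cite the separate adolescent ACQ-7 analysis, but that sentence closes the responder paragraph of SAP 2.4.4.2.1 and specifies no MMRM.

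**Conclusion.** The gap is real but minor. The fallback path is written down, ends in three common-variance structures and names no empirical variance. If UN and TOEPH both fail, the six-visit Week 12 test runs at about 4% to 9% as the assumed Week 2 SD goes from 0.55 down to 0.35 L, with the Week 12 SD held at 0.50 L. A nine-visit model to Week 24 with a 25% rise in SD gives about 8%.

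The documents do not support the inference that the primary FEV1 test will run above 5%. There is no effect if UN or TOEPH converges, and none of note if the SD is constant. Failure is more plausible in the longer models and in small subgroups, such as the roughly 84 adolescents spread over four arms. SAP 2.4.4.2.1 does not repeat the fallback, so applying it to ACQ-5 rests on the shared-method wording in the protocol and the plural in SAP Table 2.

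**What to change.** Amend the non-convergence paragraph in SAP 2.4.4.1.2 as follows:

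- After UN, use TOEPH or another structure with a separate variance at each visit, with Kenward-Roger.
- Use TOEP, AR(1) or CS only if the heterogeneous structures also fail, and then only with the empirical (sandwich) variance and a stated degrees-of-freedom method.
- State the order of the ML and covariance steps and which degrees-of-freedom method applies under ML, or drop the ML step.
- Say that the rule covers the secondary and subgroup MMRMs, and keep the planned footnote.

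The cost is a short SAP edit and one program option. The downside is that Kenward-Roger is not available with the sandwich variance, so in small subgroups such as adolescents a heterogeneous structure with Kenward-Roger should be preferred. Nothing changes if the unstructured model converges.
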